6.3 Medical history and concomitant diseases

A listing of all basic clinical data will be provided (such as prior lung diseases, smoking history, prior lung function measurements (within last 5 years), prior gas exchange measurements). These data will be collected from electronic medical records for each participant, and may not entered directly into the eCRF. All data received will be summarized as their data type suggests (see Section 3.1) by treatment arm.

The frequency of historical and ongoing conditions will be summarized by treatment (Y/N/ongoing).

Prior lung function test carried out (within last 5 years) (Y/N)

In addition to the above, any continuous data collected on lung function will be summarized by treatment arm (eg FEV1 (L)

Summary of substance use (alcohol (No, Daily, Sporadic, smoking (Never, Former, Current) or Other (No, Yes (other))) will be provided by treatment arm. Quantities may be summarized depending on quality of data provided.

6.4 Prior and concomitant medications

Prior medications include any medications that ended prior to the date of the first dose of study treatment.

Concomitant medications include medications with a start date before, on or after the first dose of study treatment and either ended post-first dose or continued after study treatment discontinuation.

Any medication that started prior to the first dose and stopped or continued after study treatment discontinuation after will be classified as both prior and concomitant.

Any medications with partially missing dates will be handled as described in [Section 4.2.3](#) to classify them as prior or concomitant.

Medication use, both prior and concomitant, and all standard of care drugs (SOC) for Arm B will be collected on eCRFs. Drugs considered as SOC and the concomitant antibiotics, as opposed to prior and/or concomitant medication, will be clearly indicated and listed and summarized as described in Section 10.1 Extent of Exposure.

If the data allow, all prior and concomitant medications will be listed for the SS by treatment group and by WHODD Anatomical Main Group [Level 1 term text], Pharmacological Subgroup [Level 3 term text] and PT. The reported term will be included in the listing. Additional endpoints to be listed will be described in the TFL shells.

Separate summaries will be presented for prior medications and concomitant medications. Prior medications which continued into the Treatment Period will also be classified as concomitant and will be included in both summaries.

If medication is not coded, then all summaries will be based on the reported term.

If coded, all tabulations will be sorted alphabetically by Level 1 term, alphabetical Level 3 term within Level, otherwise by reported term, and decreasing frequency of PT in all study participants.

A glossary of all prior and concomitant medications will be presented for the FAS including the Anatomical Main Group (Level 1), Pharmacological Subgroup (Level 3), PT and reported term.

7 MEASUREMENTS OF TREATMENT COMPLIANCE

Administration of study treatment (including the administration of appropriate antibiotics) will be performed at the study site under the supervision of the designated site personnel. Compliance will be monitored at the site through a review of the pharmacy and dispensing records to ensure that each study participant received the correct dose level.

Compliance with taking oral daily antibiotics for at least 14 days after hospital discharge in Arm A will be monitored during the planned phone call at D28. The taking of antibiotics after hospital discharge is not required for Arm B.

Any dosing deviations will be reviewed as IPDs at the DEM and assessed for possible impact on the PPS. If considered important, these deviations will be included in the summary and listing of IPDs.

8 EFFICACY ANALYSES

All raw data collected will be displayed graphically, over time (relative day as continuous and nominal day as categorical) and by treatment arm, as appropriate. Plots may be trellised by factors to explore for potential patterns if there are too many data for meaningful review in a single plot e.g. by treatment arm for each site. The y-axis may be logarithmic or natural, depending on the endpoints being visualized. Means (and 95% CI) and Median and IQ range will be included where possible on the plots – this may not be appropriate when using relative day on the x-axis, depending on the number of participants who had measurements taken on each day, but should be possible for all plots using Nominal Day on the x-axis. If the data are presented on the log scale, then the geometric mean and 95% CI will be displayed, instead of the mean and 95% CI.

Of general note, since the protocol is not written using an estimand framework, this SAP will describe primary analyses for both primary and secondary endpoints. In addition, some pre-planned sensitivity and supplementary analyses are described.

In this context a sensitivity analysis is an additional analysis carried out on the same endpoint to determine how robust inferences based on the endpoint are to limitations in the data and assumptions behind the model used in the primary analysis. The analyses could use different transformations of the raw data, using different variance-covariance structures and different methods for handling missing data.

A supplementary analysis to support any clinical inference could use different methods of statistical analysis and/or different, but related, endpoints.

8.1 Statistical analysis of the primary efficacy endpoint(s)

The primary efficacy endpoints are PaO₂/FiO₂ ratio, P(A-a) O₂ gradient and a/A PO₂ ratio and of interest are comparisons between treatments of:

- Change from baseline to nominal D6 in PaO₂/FiO₂ ratio (units=mm Hg)
- Change from baseline to nominal D6 in P(A-a) O₂ gradient (units=mm Hg)
- Change from baseline to nominal D6 in a/A PO₂ ratio (unitless)
- Change from baseline to nominal D15 in PaO₂/FiO₂ ratio
- Change from baseline to nominal D15 in P(A-a) O₂ gradient
- Change from baseline to nominal D15 in a/A PO₂ ratio

Mapping of results to nominal days in the event that a participant is discharged from hospital before nominal D6 and/or nominal D15 is described in Section 3.2.1.3.

Residual plots, including plots against potential covariates, will be produced to investigate the validity of the assumptions behind the analyses for each of the 3 primary endpoints and if necessary, sensitivity analyses will be carried out (Section 8.1.3). Results from the most appropriate analysis will be presented.

8.1.1 Derivations of primary efficacy endpoint(s)

Measurements to derive PaO₂/FiO₂ ratio (measure of severity of hypoxemia), P(A-a) O₂ gradient (always positive and a reflection of the difficulty oxygen has at crossing the alveolar capillary membrane and increases with age and FiO₂ related to determine if it is normal.) and a/A PO₂ ratio are to be taken at Baseline, and at least at pre-dose (for arm A) on Day 6 and Day 15 (or at discharge, whichever comes first). Measurements for Arm B can be taken at any time, but preferably at the same time on each Day for every participant to allow for diurnal variation, at least on Days 1, 6, 15 (or at discharge, whichever comes first). Where possible, more frequent measurements will be taken in both arms, preferably daily.

eCRFs indicate that FiO₂ will be taken daily, however PaO₂ and PaCO₂ only at Screening/Day-1, nominal D1, nominal D6 and nominal D15.

Therefore, the derived parameters should be calculated using the data from the arterial blood gas (ABG) eCRF and not from Vital Signs.

Calculation

PaO₂ is the partial pressure of oxygen in the **arterial blood** and provided on the CRF. The Alveolar Gas Equation provides an estimate of PAO₂.

$$\text{PAO}_2 = (\text{P}_{\text{atm}} - \text{P}_{\text{H}_2\text{O}}) \text{FiO}_2 - \text{PaCO}_2 / \text{RQ}$$

(=partial pressure of oxygen in the **alveoli**)

Where:

P_{atm} is atmospheric pressure at sea level = constant 760 mm Hg

P_{H₂O} is partial pressure of water in alveoli = constant 45 mm Hg

F_iO₂ is fractional concentration of O₂ in inspired air, from eCRF (or 21% (0.21) if participant is not on supplemental oxygen

PaCO₂ is partial pressure of carbon dioxide in alveoli from eCRF

RQ = respiratory quotient = constant 0.82 (for typical human diet)

$$\text{P(A-a) O}_2 \text{ gradient} = \text{A-a gradient} = \text{PAO}_2 - \text{PaO}_2$$

$$\text{a/A PO}_2 \text{ ratio} = \text{PaO}_2 / \text{PAO}_2$$

Given that ABG is only measured on specified days, change from baseline to each of these days will be calculated for each of these endpoints for each participant [For example, (D6 - Baseline), (D15 - Baseline)].

Note:

All the above calculations should be carried out and used to verify the result for variables that are directly collected on the eCRF. Any discrepancy should be listed but the ones on the eCRF should be primarily used.

Increasing values for PaO₂/F_iO₂ ratio indicates improvement over time (normal considered ~470 mmHg)

Decreasing values of P(A-a) O₂ gradient indicates improvement over time (normal A-a gradient is (Age/4) +4) and in addition increases with higher F_iO₂

No similar statement for a/A PO₂ is appropriate.

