4.1. Primary End Points + Time Points

To measure the effectiveness of SC Zilucoplan® treatment on restoring lung homeostasis, the **primary endpoint** of this intervention is **measuring oxygenation** at predose day 6 and day 15 (or at discharge, whichever comes first) through assessment of the mean and/or median change from pretreatment (day 1) to post-treatment (day 6 and 15 or at discharge, whichever comes first) PaO₂/FiO₂ ratio, P(A-a)O₂ gradient and a/A pO₂ ratio, which can easily be performed in the setting of clinical observation of patients admitted to the COVID-19 ward or ICU COVID-19 unit. These measurements derived from an arterial blood gas sampling are taken when the patient is sitting upright and breathing room air. Since supplemental oxygen will be indispensable in some patients, the A-a gradient will be normalized against age and FiO₂ expected A-a gradient, according to validated formulas. If patients leave hospital between day 6 and day 15, that day of discharge will be taken as measurement point for primary endpoint instead of day 15. For patients on ECMO the PaO₂/FiO₂ ratio and Aa-gradient cannot be calculated as in this case the FiO₂ will be missing. Therefore, the last available value of PaO₂/FiO₂ ratio and Aa gradient prior to ECMO can be used at that timepoint.

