11.2. Type of statistical methods

All primary and secondary endpoints will be summarized and where relevant represented graphically

Primary endpoint:

The change from baseline in PaO₂/FiO₂ ratio will be analyzed using a Mixed Model Repeated Measures (MMRM) analysis with a fixed effect for Baseline PaO₂/FiO₂ ratio, treatment, day and treatment by day interaction, where day is categorical. Subject will be fitted as a random effect and an unstructured covariance will be used unless it fails to converge, where other covariance structures will be considered. Other covariates, such as gender, may also be included in the model, if by the time of the analysis these have been identified as key differentiators in terms of COVID-19 recovery. If the variability is shown to be inappropriate for this additive model, then a log transformation of the PaO₂/FiO₂ ratio may be considered.

Data from SOC in another study with a very similar protocol may be incorporated into the analysis using a Bayesian frame work. This will be described more fully in the statistical analysis plan (SAP).

A similar analysis for the P(A-a)O₂ gradient will be completed

Other Endpoints:

Other continuous endpoints will be analyzed in a similar way using an MMRM.

Response rates, such as 28 day all-cause mortality a logistic regression will be used.

Count data will use a generalized linear model with a log link unless the model is either over or under dispersed and then an alternative approach will be used. If it is counts out of a fixed number of days, then a logistic regression will be considered.

For the final follow up, a survival analysis with Kaplan-Meir plots will be created covering from Day 1 to end of follow up.

The detail around the analyses will be explained in more detail in the SAP and as this is an exploratory study, additional analyses may be considered to explore the data more fully.

Interim analyses: will be performed when 42 patients have reached primary endpoint analysis.

After half the patients have completed day 15 an interim analysis will be completed to understand if there is already enough evidence to prompt further work on COVID-19 treatment with Zilucoplan®. There is no plan to stop the study at this stage.

Analyses will also be completed when all patients have finished day 28 to assess all pre-follow up assessments and 28 day mortality (via phone call). This will enable key results to be understood as soon as possible without compromising the study.

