3.8 Changes to protocol-defined analyses

The analysis of the primary endpoint described in the protocol omitted to add that baseline*day would be included as a fixed effect in the Mixed Model Repeated Measures (MMRM) analysis. This is needed in order to account for the fact that values from days closer to baseline are likely to be more correlated than values at days further apart from baseline. This is important if we include D28 and long-term follow-up in some of our analyses.

The primary analyses will be using Nominal Day as the categorical time point, and not strict relative day. This is because whilst the ideal is to take measurements as frequently as possible, the protocol only specifies specific days, which are the primary days for comparing between treatment arms. Therefore, windowing has been incorporated into the derivation of Nominal Day to ensure data that may not have been collected on the specific day of interest, but are within the window, are used. Sensitivity analyses using Relative Day (continuous and/or categorical) will be carried out as described in the relevant sections.

An additional variable will be created to indicate day of discharge and where needed, the results on the day of discharge will be mapped to the appropriate nominal day (Section 3.2.1.3).. This is to match with the sentence in Section 7.1.2 where it describes how to treat data if the day of discharge is prior to D15.

The SAP will not be amended for any changes to planned analyses or any additional analyses that are made after database lock

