4.5 Multiple comparisons/multiplicity

Three endpoints are listed that are associated with the primary objective. There are no plans to control for multiplicity in the primary objectives as the endpoints are different parameterizations of the same underlying endpoint measured on separate days. This means there is effectively only one primary endpoint, PaO₂/FiO₂ ratio which was used to calculate sample size. The comparison of the differences from baseline to two days (D6/Early Discharge and D15/Early discharge) are of specific interest.

There are no plans to control for multiplicity in the secondary objectives as these hypotheses are considered exploratory. Therefore, any findings will need to be confirmed in subsequent studies.

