8.1.2 Primary analysis of the primary efficacy endpoint(s)

Summary descriptive statistics for each endpoint and change from baseline for each endpoint, including to follow-up, will be provided by treatment and Nominal Day (D1(Baseline), D2, D6, D15 and Follow-Up).

Each endpoint (PaO₂/F_iO₂ ratio, P(A-a)/O₂ gradient, a/A PO₂ ratio) will be analyzed separately using a Mixed Model Repeated Measures (MMRM) analysis with fixed effects for Baseline, treatment, Nominal Day (using Nominal Days, D6 and D15), Baseline*Nominal Day interaction and treatment*Nominal Day interaction where Nominal Day is categorical. Participant will be fitted as a random effect and an unstructured covariance will be used, unless it fails to converge,

when other covariance structures will be considered. Mean change from baseline to D6 and D15 for each treatment arm and differences between treatments in mean change from baseline to D6 and D15, their 95% confidence intervals and p-values will be estimated directly from the model.

The primary analysis will not adjust for missing data, other than how they are handled in MMRM under the assumption that the data are missing at random. This assumption implies that the behaviour of the post dropout observations can be predicted from the observed endpoints, and therefore the response can be estimated without bias using exclusively the observed data.

The following results from the model will be tabulated:

- LSMEANS (adjusted for baseline levels) and 95% confidence intervals for change from baseline by treatment and Nominal Day for each endpoint (PaO₂/FiO₂ ratio, P(A-a)/O₂ gradient, a/A PO₂ ratio)
- Estimates of the differences between treatments in mean change from baseline, 95% confidence interval and p-value at D6 and D15 for each endpoint (PaO₂/FiO₂ ratio, P(A-a)/O₂ gradient, a/A PO₂ ratio).
- Mean percentage change from baseline will be estimated from the results of the MMRM model for D6 and D15 for each Treatment Arm, together with 95% confidence intervals.

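### The protocol normalises the A-a gradient for age and FiO₂; the SAP tests the raw gradient and does not declare the change

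*SAP*

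**What the plan says.** **Protocol.** Section 4.1 states: "Since supplemental oxygen will be indispensable in some patients, the A-a gradient will be normalized against age and" the gradient expected at that FiO₂, by validated formulas that it does not name. The synopsis also has the word normalised in its primary endpoint. Section 11.2 says only "A similar analysis for the P(A-a)O₂ gradient will be completed", after describing the mixed model for PaO₂/FiO₂, and does not repeat the normalisation.

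**SAP derivation.** Section 8.1.1 defines the gradient as PAO₂ − PaO₂. It remarks that the gradient "increases with age and FiO₂ related to determine if it is normal", and later that a decreasing "gradient indicates improvement over time (normal A-a gradient is (Age/4) +4) and in addition increases with higher" FiO₂. These are notes on interpretation and do not enter the derivation. Of the third endpoint it says: "No similar statement for a/A PO₂ is appropriate".

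**SAP analysis.** Section 8.1.2 fits baseline, treatment, day, baseline by day and treatment by day, and reports "Estimates of the differences between treatments in mean change from baseline, 95% confidence interval and p-value at D6 and D15 for each endpoint". Section 8.1.3 repeats the models with age among the added covariates, but not FiO₂.

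**SAP declared changes.** Section 3.8 begins "The analysis of the primary endpoint described in the protocol omitted to add that baseline*day would be included as a fixed effect". It goes on to nominal-day windows and the mapping of discharge-day results. The dropped normalisation is not there.

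**SAP multiplicity.** Section 4.5 says: "There are no plans to control for multiplicity in the primary objectives as the endpoints are different parameterizations of the same underlying endpoint".

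**The concern.** The protocol gives a reason for normalising, and the SAP repeats the physiology behind it. The quantity that the SAP tests nevertheless lacks the correction, and the section meant for declaring such changes is silent. By the SAP's own equation the raw gradient scales with FiO₂, so a patient sampled at a lower FiO₂ than at baseline can show a smaller gradient with unchanged or worse gas exchange.

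The plan allows FiO₂ to differ between samples. Ventilated patients are sampled at the ventilator setting (protocol 9.2 and the footnotes to 9.4), and protocol 4.1 itself expects some patients to need oxygen throughout. Off-oxygen sampling is mandatory in the footnote attached to Day 6 and Day 15, but only strongly recommended in the entry criterion (6.1).

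At stake is how the gradient result is read. One of three endpoints described as versions of the same thing could point the opposite way from the other two, and the SAP has no rule for that case. The SAP also declines to give a direction for a/A, which would help to settle such a conflict.

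**Working it through.** **1. The plan's own figure.** Protocol 11.1 and SAP 2.4 claim more than 85% power for an 80-point difference in PaO₂/FiO₂ with SD 105, 54 v 27 participants, two-sided 5%.
- All 81: standard error 105 × √(1/54 + 1/27) = 24.75; 80/24.75 = 3.23; power Φ(3.23 − 1.96) = 89.8%.
- After 10% dropout (48.6 v 24.3): standard error 26.09; power 86.6%.
- The noncentral t gives 89.1% and 85.7%.

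The claim reproduces. It concerns PaO₂/FiO₂ only; no power is stated for the gradient.

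**2. The SAP equation.** With atmospheric pressure 760, water vapour 45 and RQ 0.82 (SAP 8.1.1), PAO₂ = 715 × FiO₂ − PaCO₂/0.82. PaCO₂ of 40 mmHg, equal at both samples, is my assumption.

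| | Baseline | Follow-up |
|---|---|---|
| FiO₂ | 0.60 | 0.40 |
| PaO₂/FiO₂ | 300 | 200 |
| PaO₂ | 180 | 80 |
| PAO₂ | 429 − 48.8 = 380.2 | 286 − 48.8 = 237.2 |
| Gradient | 200.2 | 157.2 |
| a/A | 180/380.2 = 0.473 | 80/237.2 = 0.337 |

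The gradient falls by 43.0 mmHg while both ratios worsen. PaCO₂ cancels in the change if it is equal at both samples, so −43.0 also holds at 30 or 50 mmHg.

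**3. How far this goes.** Writing r for PaO₂/FiO₂, the gradient is (715 − r) × FiO₂ − PaCO₂/0.82.
- Same FiO₂ step from r = 300: the gradient is unchanged when (715 − r₂) × 0.40 = 415 × 0.60, so r₂ = 92.5. It registers worsening only below that.
- Unchanged r = 150, FiO₂ 0.60 to 0.40: the change is −(715 − 150) × 0.20 = −113 mmHg.
- Both samples on room air: the FiO₂ effect is zero.

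**4. The age part.** SAP 8.1.1 gives Age/4 + 4, which is 14 at age 40 and 24 at age 80. Subtracted at both visits, it cancels and the −113 above is unchanged. Used as a divisor it does not: −113/14 = −8.07 and −113/24 = −4.71. Protocol 4.1 does not say which form applies.

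**5. Arm comparison (illustrative).** I simulated 54 v 27 with no treatment effect, FiO₂ 0.41 or 0.21, follow-up a/A equal to baseline plus noise (SD 0.06), and change regressed on arm and baseline gradient.
- *Baseline imbalance*, on-oxygen samples 35% v 25%, follow-up on room air: with baseline a/A 0.50 to 0.75 the arm difference is −5.4 mmHg unadjusted and −0.6 adjusted. About 65% of those on-oxygen baselines would exceed a PaO₂/FiO₂ of 350, the entry limit in protocol 6.1. Restricting a/A to 0.50–0.587 respects the limit, and the adjusted shift is then about 0.1.
- *Follow-up imbalance*, 25% v 15%, baseline on room air: PAO₂ rises by 715 × 0.20 = 143, so the shift is about 0.10 × 143 × (1 − 0.625) = 5.4 mmHg. Simulation gives 5.3 with or without adjustment. In the restricted range it is about 6.5.

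The 10-point imbalances are assumed, and the simulation makes oxygen use independent of gas exchange.

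**The case against.** The case for leaving the plan alone has several parts.

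- **PaO₂/FiO₂ carries the trial.** SAP 4.5 says there is effectively one primary endpoint, the one used for sample size. This stands, and it limits the harm to the reading of the gradient.
- **Most samples should be off oxygen.** The Day 6 and Day 15 footnote makes this mandatory outside ventilation, so the effect may be confined to a minority. This stands; the share is unknown.
- **The example is constructed.** PaO₂ falls from 180 to 80 while FiO₂ is lowered, and the break-even corresponds to a PaO₂ of 0.40 × 92.5 = 37 mmHg. True: it shows that the direction can reverse, not that it usually does.
- **The SAP carries the caveat.** The FiO₂ warning is in the same sentence as the statement on improvement. A reader might infer that the SAP takes every fall as improvement, and the text does not support that. But the warning leads to no rule in the analysis.
- **Other safeguards.** SAP 4.1 may add baseline ordinal category, and SAP 8.1 plots residuals against potential covariates. Neither brings in FiO₂ at follow-up.
- **The value on the eCRF takes priority and might be normalised.** No document says so, and the SAP's checking formula is the raw difference.
- **The SAP cites protocol version 3.0.** That text is not available. The visible change log for versions 4.0 to 6.0 lists nothing on normalisation.
- **The protocol names no formula and 11.2 does not repeat the step.** That is a reason to specify or declare, not to stay silent.

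**Conclusion.** The departure is real and undeclared. The protocol promises a gradient normalised for age and FiO₂; the SAP derives, models and tests the raw one. Of the two missing corrections, FiO₂ matters more, since a subtractive age correction cancels in a change score. Where FiO₂ differs between samples, the raw gradient can fall (by 43 mmHg in the example) while PaO₂/FiO₂ and a/A worsen, which does not fit the reasoning in SAP 4.5. The statement on a/A is also wrong: PaO₂/PAO₂ makes a higher value better.

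Three stronger readings are not supported. A reader might infer that the between-arm gradient comparison is biased by a known amount. The documents give neither the share affected nor any imbalance, baseline adjustment absorbs most of a baseline FiO₂ imbalance, and a follow-up difference in FiO₂ may partly be real oxygen need. A reader might infer that the trial's main result or power is compromised; the PaO₂/FiO₂ analysis and its power are unaffected. A reader might conclude that the gradient should lose its test and a/A stand in for it. That would be a further departure from protocol 11.2, would leave the gradient primary in SAP 2.2.1.1 and 8.1 with p-values through SAP 3.1 and 8.1.3, and would rely on a ratio with no age correction.

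The sizes rest on the SAP constants and assumed gas values.

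**What to change.** 1. **Preferred.** In SAP 8.1.1, write in the validated formula that protocol 4.1 refers to, derive the gradient normalised for age and FiO₂, and use it in the models of 8.1.2 and 8.1.3. Subtracting Age/4 + 4 alone is not enough. If the formula subtracts an expected value, the result need not be positive, so check the log-scale model in 8.1.3.
2. **If no formula is available.** Keep the raw-gradient mixed model, as protocol 11.2 plans. Declare in SAP 3.8 the departure from protocol 4.1 and the synopsis. State that a fall in the raw gradient is read as improvement only when FiO₂ at sampling is comparable with baseline, or when a/A and PaO₂/FiO₂ agree.
3. **In either case.** Replace "No similar statement for a/A PO₂ is appropriate" with a statement that a higher a/A ratio indicates improvement. Tabulate, by arm and nominal day, the share of participants whose FiO₂ at sampling differs from baseline.

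The cost is one decision on the formula, some SAP wording and one small table. Protocol 9.2 already has FiO₂ at the time of the blood gas recorded in the eCRF (except on ECMO), so no new data are needed.
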